#### 4.1.2. Treatment Period

Participants will initiate outpatient dosing beginning on Day 1 (the day after the Baseline Visit). During the 2-week Titration Period, the participant's dose will be increased in a blinded fashion up to the randomized dose level (darigabat 25 mg BID or placebo BID). In the darigabat 25 mg BID group, darigabat will be administered as 5 mg BID for 1 week followed by 12.5 mg BID for another week during the Titration Period, and then 25 mg BID during the 12-week Maintenance Treatment Period. A summary of the dosing schedule is provided in [Table 3](#).

**Table 3: Dosing Schedule**

Blinded Treatment Assignment	Titration Period		Begin Target Dose
	Day 1-7	Day 8-14	Day 15
Darigabat 25 mg BID	5 mg BID	12.5 mg BID	25 mg BID
Placebo	Matching Placebo	Matching Placebos	Matching Placebo

Abbreviation: BID=twice daily.

Participants will continue to record all requested information in the eDiary for each day during both the 2-week Titration and 12-week Maintenance Treatment Periods.

#### 4.1.3. Follow-up Period

Follow-up telephone contacts will be performed within 3 days and 7 days after the last dose of IMP and an in-clinic follow-up visit will be performed approximately 33 days after the last dose of IMP. The PWC will be used to monitor for withdrawal symptoms approximately 3 days and 7 days after the last dose of IMP. Participants will continue to record all requested information in the eDiary for each day up to 7 days after the last dose of IMP. Participants should not begin taking their standard-of-care treatment for up to 7 days after the last dose of IMP, if possible.

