1.2. Schema

A schematic of the trial design is provided in [Figure 1](#).

Figure 1: Trial Schematic

Abbreviations: BID=twice daily; R=randomization.

Note: A summary of the dosing schedule, including doses during the Titration Period, is provided in [Table 3](#).

a Randomization occurs at Baseline (Visit 2).

b Visit 7 (Telephone) and Visit 8 (Telephone) will occur 3±1 days and 7±3 days after Visit 6, respectively.

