h Full physical and neurological examinations should be completed at Screening. Limited examinations (cardiovascular, pulmonary, and gastrointestinal) should be completed at all other specified time points. Symptom-driven physical and/or neurological examinations may be done at any time during the trial at the investigator's discretion.

- i 12-lead ECG assessments will be performed after the participant has been at rest for approximately 3 minutes. At Screening, the average of 3 consecutive ECGs collected 1 to 2 minutes apart will be used to determine participant eligibility; at Baseline, only 1 reading is required for determination of eligibility. Single ECGs will be obtained at all other time points. Additional ECGs can be performed at the investigator's discretion (eg, if abnormalities are noted).
- j Blood pressure and heart rate assessments should be performed in order to confirm eligibility (see Exclusion Criterion in [Section 5.2](#)). Triplicate supine heart rate and blood pressure measurements should be taken at approximately 1-minute intervals at the Screening Visit. Duplicate supine heart rate and blood pressure measurements will be taken at all other time points. The supine heart rate and blood pressure measurements will be followed by a single measurement after approximately 2 minutes in a standing position to allow for orthostatic assessments. Additional time points can be added at the investigator's discretion (eg, if abnormalities are noted). Further details are provided in [Section 8.2.3](#) and in the Operations Manual.
- k Visit 6 will be considered the baseline assessment for the PWC.
- l Prior and concomitant medications, including cannabis products, should be recorded from Screening through the participant's last visit/contact.
- m Adverse events (serious and nonserious) should be recorded from the first dose of IMP on Day 1 (eg, the day after Baseline) through the participant's last visit/contact.
- n For women of childbearing potential only. Pregnancy tests can be performed at any time during the trial at the discretion of the investigator if pregnancy is suspected. Any urine pregnancy tests that are positive must be confirmed using a serum test.
- o Additional urine drug screening can be conducted at any time during the trial at the discretion of the investigator.

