- p Reflex viral hepatitis C PCR testing if hepatitis C antibody is positive or indeterminate.
- q A confirmatory FSH is required for all postmenopausal women.
- r With participants maintaining their normal BID dosing routine, a single daytime blood sample for determination of plasma darigabat concentration will be collected at Visits 3, 4, 5, and 6. The date and time of the PK sample, as well as the time of ingestion of previous dose of IMP, will be recorded in the source documentation.
- s Future biospecimen research sample is optional and is only to be collected if signed consent is obtained from the participant. Sample can be collected at any time following confirmation of participant eligibility and prior to initiation of first dose.
- t Randomization will occur at Baseline and IMP will be dispensed after randomization. Participants will start taking IMP on Day 1 (eg, the day following their Baseline Visit). Dosing will continue through Visit 6 (Day 98) or ET.

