## **6.7. Prior and Concomitant Therapy**

### **6.7.1. Time Period for Recording Prior and Concomitant Therapy**

The investigator will record all therapies (including vaccines, over-the-counter or prescription medicines, vitamins, and/or herbal supplements) taken by the participant from 30 days prior to signing the ICF through the end of the evaluation period (defined as the time period during which participants are evaluated for primary and/or secondary objectives).

For concomitant medications, the following information will be recorded in the eCRF: medication, indication, dose, frequency, route, start date, and end date. For nondrug therapies or procedures, the following information will be recorded in the eCRF: therapy/procedure name, indication, start date, and end date.

The medical monitor should be contacted if there are any questions regarding concomitant or prior therapy.

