**Table 6: Prohibited Concomitant Medications and/or Therapies**

Prohibited Concomitant Medications/Therapies During Trial Conduct

All psychoactive substances (unless otherwise noted) including but not limited to:
 
 
• Antidepressants
 
• Opiates
 
• Anxiolytics (eg, benzodiazepines, non-benzodiazepine anxiolytics)
 
• Beta receptor antagonists used for any indication
 
• Antiseizure/neuropathic pain medications used for any indication (eg, gabapentin, pregabalin, topiramate, phenytoin, phenobarbital)
 
• All first-generation antihistamines are prohibited for all indications, except for diphenhydramine, which is permitted only if medically indicated for insomnia and used no more than 3 times per week.
 
• Hypnotics 
 
○ Sleep medications (eg, zolpidem, zaleplon, eszopiclone, trazodone, and suvorexant or other orexin receptor antagonists) are permitted if medically prescribed at doses labeled for insomnia and used no more than 3 times per week
 
 
 
• Mood stabilizers (eg, lithium, divalproex, carbamazepine, lamotrigine)
 
• Stimulants (eg, amphetamine, methylphenidate, modafinil)
 
• Antipsychotics
 

D2/3 agonists (eg, pramipexole)
Any OTC treatments for the treatment of panic disorder or anxiety disorder(s) (eg, cannabis products/THC, CBD a , herbal supplements, including but not limited to valerian root, St. John's wort, and GABA supplements)
Investigational agents
Any drug or product that is a moderate to strong inducer of CYP3A4 metabolism, which has the potential to lower darigabat exposure levels. An example list of strong (>80% reduction in AUC) and moderate (50% to 80% reduction in AUC) inducers is provided in Section 10.7 .
Any drug or product that is classified as a significant (ie, strong or moderate) inhibitor of the CYP3A4 metabolic pathway, which has the potential to increase darigabat exposure levels. An example list of strong (eg, >5-fold increase in AUC) and moderate (eg, 2-to 5-fold increase in AUC) inhibitors is provided in Section 10.7 .
BCRP substrate rosuvastatin
Exposure-based therapy
Systemic steroids are prohibited. Any steroid that is not systemic (eg, topical or inhaled) is permitted.

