### **7.2. Participant Discontinuation/Withdrawal From the Trial**

All participants have the right to withdraw from the trial at any time without prejudice. Participants cannot withdraw consent for use of data already collected as part of the trial, but can withdraw consent for future participation. The investigator can also discontinue a participant from the trial at any time for safety, behavioral, or compliance reasons. Unless a participant provides written withdrawal of consent or there is other written documentation by the investigator confirming the participant's verbal intent to completely withdraw from the trial, participants should be followed for all protocol-specified evaluations and assessments, if possible.

At the time of discontinuation from the trial, if possible, an early termination visit should be conducted. Unless a participant withdraws consent, an Early Termination Visit and end of trial procedures should be conducted if a participant discontinues IMP. Unless clinically necessary, the initiation of any prohibited medications should occur after the completion of all of the assessments at the Early Termination Visit and Telephone Visits 7 and 8. See the Schedule of Assessments ([Section 1.3](#)) for data to be collected at the time of discontinuation and follow-up and for any further evaluations that need to be completed.

The reason for discontinuation from the trial will be recorded in the eCRF.

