3.2.6. Prior and Concomitant Medications

Prior medications are those medications taken prior to and ended prior to the initiation of IMP. Concomitant medications are those medications taken on or after the initiation of IMP. These medications include those medications started before the initiation of IMP and continuing post Day 1. These medications will be recorded in the PRIOR AND CONCOMITANT MEDICATIONS eCRF. Medications that start after the last dose of IMP will be classified as taken post last dose and will not be considered as concomitant.

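### The PWC withdrawal summary can include scores taken after a participant has restarted a fast-acting anxiolytic, and the SAP text has no flag for this

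*Protocol*

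**What the plan says.** **The hold.** Protocol 4.1.3, repeated in the Synopsis and SAP 1.4, reads: "Participants should not begin taking their standard-of-care treatment for up to 7 days after the last dose of IMP, if possible".

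**The visits.** Table 1, footnote t: "Dosing will continue through Visit 6 (Day 98) or ET". Schema, footnote b: "Visit 7 (Telephone) and Visit 8 (Telephone) will occur 3±1 days and 7±3 days after Visit 6, respectively". Table 1 places the PWC at Visit 6 (its baseline), Visit 7 and Visit 8. Section 4.1.3 also describes the calls as falling within 3 and 7 days of the last dose, and Section 4.2 describes PWC monitoring as lasting no more than 7 days.

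**Other limits on medication.** Section 7.2 says that, unless clinically necessary, the start of prohibited medication "should occur after the completion of all of the assessments at the Early Termination Visit and Telephone Visits 7 and 8". That sentence belongs to the discontinuation rules. Table 6 covers anxiolytics, including benzodiazepines, under the title "Prohibited Concomitant Medications/Therapies During Trial Conduct", and gives no end day.

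**The analysis.** SAP 3.2.6: "Medications that start after the last dose of IMP will be classified as taken post last dose and will not be considered as concomitant". SAP 5.17.2 summarises prior and concomitant medications and lists all medications. SAP 5.18.3 lists PWC items and totals and summarises the total by treatment group. It does not mention restarted medication or days since the last dose.

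**The data available.** Table 1, footnote l: "Prior and concomitant medications, including cannabis products, should be recorded from Screening through the participant's last visit/contact". Section 6.7.1 requires, for each concomitant medication, "medication, indication, dose, frequency, route, start date, and end date".

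**The concern.** Withdrawal symptoms by PWC are a named safety endpoint, and Visit 8 is the last PWC assessment. The protocol says that darigabat binds at the benzodiazepine site (2.2.2), describes the PWC as a measure of benzodiazepine-like withdrawal (4.2), and notes that benzodiazepines are used when rapid symptom control is needed (2.2.1). A participant who restarts one before a PWC call may score lower because of it.

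Participants with the worst symptoms have the most reason to restart, so the plausible direction is to hide withdrawal. If withdrawal occurs mainly on darigabat, the masking would fall mainly in that group and narrow the difference from placebo. A reader of the summary table would have no sign of this.

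**Working it through.** **Inputs.** Last dose at Visit 6, nominally Day 98 (Table 1, footnote t). Visit 7 at 3±1 days and Visit 8 at 7±3 days after Visit 6 (Schema, footnote b). Hold through day 7 after the last dose (4.1.3).

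**1. The plan's own figure.** 98 + 7 = Day 105. 105 − 3 = Day 102 and 105 + 3 = Day 108. This agrees with Day 105 ±3 in Table 1. Day 108 is also the upper Visit 8 limit in SAP Table 10, which applies to early-termination and unscheduled records. Scheduled visits map to the nominal visit under SAP 4.3.

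**2. Permitted days against the hold.** Days after the last dose, if the last dose is on the day of Visit 6:

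| Visit | Permitted days | After the hold (day > 7) |
|---|---|---|
| Visit 7 | 2, 3, 4 | 0 of 3 |
| Visit 8 | 4, 5, 6, 7, 8, 9, 10 | 3 of 7 (days 8, 9, 10) |

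With Visit 6 on Day 98, the three days are Study Days 98 + 8 = 106 to 98 + 10 = 108.

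**3. Sensitivity.** If Visit 6 falls on Day 95 or Day 101 and Visit 8 is counted from the actual Visit 6, the result is again 3 of 7. If the last dose was taken the day before Visit 6 (an assumption), the window is days 5 to 11 and 4 of 7 days come after the hold.

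**4. Restarts inside the hold.** The hold is a request, not a rule. A tolerated restart on days 1 to 7 can precede a Visit 7 call or a Visit 8 call on any of their permitted days. Days 8 to 10 are therefore only part of the exposure.

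**5. What the SAP does with such a case.** Take a benzodiazepine started on day 5 or day 9, followed by an in-window Visit 8 call.
- The drug starts after the last dose, so it is not concomitant (3.2.6).
- It is therefore in neither medication summary and appears only in the listing (5.17.2).
- The PWC score is mapped to Visit 8 (4.3) and enters the total-score summary (5.18.3).
- No step in the SAP text joins the two records.

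**6. Check of the corrected hold.** Let the hold end on day min(10, max(7, day of Visit 8 PWC)). A PWC on day 4 gives day 7, on day 8 gives day 8, and on day 10 gives day 10. No permitted Visit 8 day then follows the hold (0 of 7), and the extra hold is at most 10 − 7 = 3 days. If the last dose was the day before Visit 6, day 11 remains outside (1 of 7).

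**The case against.** The best case for the plan has four parts.

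- **Intended timing.** Sections 4.1.3 and 4.2 place the calls and the PWC within 7 days, so the extra 3 days are only a scheduling tolerance. This stands as intent. The same section also gives the PWC days as approximate, and the schedule that sites follow allows day 10.
- **Table 6 bars anxiolytics anyway.** Read literally, it could run to Visit 9 (Day 131), and rescue benzodiazepine use requires contact with the medical monitor. A 7-day hold would then have little purpose for those drugs. The protocol is ambiguous, rather than clearly protective or clearly permissive.
- **The records are visible.** All medications are listed and PWC scores are listed by visit, so a restart can be found by hand. The output shells are in a separate document that is not available, so a flag there cannot be ruled out. This stands, and limits the point to the SAP text.
- **Few cases.** Section 2.2.1 calls SSRIs and SNRIs first-line. An SSRI begun on day 8 is unlikely to change a score by day 10. This also stands: the concern is fast-acting drugs.

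A reader might infer that 3 of 7 means about 43% of Visit 8 scores are compromised. It does not. These are calendar days, and the documents give no call-day or restart data. Nor do the documents show that the protocol authorises anxiolytics on days 8 to 10, that the PWC results are biased, or that efficacy is touched.

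**Conclusion.** The point holds as a minor one. PWC scores taken after a restart can enter the withdrawal summary unmarked. One reason is that the hold tolerates restarts on days 1 to 7. The other is that, for completers, days 8 to 10 are in the Visit 8 window but after the hold. The day count assumes that the last dose is taken on the day of Visit 6. The number of affected scores and the size of any effect on them cannot be computed from the documents.

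The consequence is confined to a descriptive safety endpoint. Power, type I error and the efficacy endpoints are unaffected. After the early closure described in SAP 6, participants taken off treatment early fall under 7.2, so the days 8 to 10 gap concerns only those who completed Visit 6. Restarts under the clinical-necessity exception in 7.2 would also go unmarked in the PWC summary.

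**What to change.** **Main change, SAP 5.18.3.**
- Keep all observed PWC data as the main summary.
- Flag any PWC taken after the start of a post-last-dose psychoactive medication.
- Report days since last dose at Visits 7 and 8.
- Add a supportive descriptive summary without the flagged scores. Note beside it that a restart may itself be caused by withdrawal, so leaving those scores out can understate withdrawal.

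This costs one derived flag and one table, from start dates already collected. If it is added after the SAP is final, SAP 6 already provides for documenting the deviation in the study report.

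**Secondary change, Protocol 4.1.3, the Synopsis and SAP 1.4.** Unless clinically necessary, no standard-of-care or prohibited medication until the later of day 7 after the last dose and completion of the Visit 8 PWC, and no later than day 10. The day 7 floor matters: a hold tied to Visit 8 alone could end on day 4, while eDiary recording continues to day 7. This costs one sentence in three places and up to 3 more days of hold for some symptomatic completers. It has little practical use in this trial after early closure, but would suit a future protocol. The flag would cover what it leaves open, such as a call on day 11 when the last dose preceded Visit 6.

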#### 4.1.4. Definition of Completed Participant

A participant is considered to be a treatment completer if he/she has completed the Treatment Period of the trial including the last visit in the Maintenance Treatment Period (Visit 6, Day 98).

A participant is considered to have completed the trial if he/she has completed all periods of the trial including the last scheduled procedure in the Safety Follow-up (Visit 9, Day 131) as shown in the Schedule of Assessments in [Section 1.3](#).

## 4.2. Scientific Rationale for Trial Design

The randomized, double-blind, placebo-controlled, parallel-group trial design minimizes the risk of bias and is considered appropriate for evaluating the effects of a trial treatment for indications in which use of a placebo is acceptable ([US FDA, 2001](#)). Randomization reduces bias in the assignment of participants to a treatment group, the double-blind design prevents differential treatment and assessments, and the placebo-controlled design controls for all potential influences on the actual or apparent course of the disease other than those arising from the pharmacologic action of the drug.

The 12-week Maintenance Treatment Period is selected to allow sufficient opportunity to characterize the effect of darigabat. In addition, the Treatment Period is equivalent to or longer than the duration used in previous clinical trials evaluating treatments for panic disorder, in which the duration ranged from 6 weeks to 12 weeks ([Nardi et al, 2011](#); [Liebowitz et al, 2009](#); [Pollack et al, 2007](#); [Bradwejn et al, 2005](#); [Pollack et al, 2003](#); [Goddard et al, 2001](#); [Michelson et al, 2001](#); [Schweizer et al, 1990](#); [Munjack et al, 1989](#); [Chouinard et al, 1982](#)).

The dose planned for investigating the efficacy of darigabat for the treatment of panic disorder is 25 mg BID based on the results from the Phase 1 Trial CVL-865-HV-001 and considering the

PK, estimated  $\alpha 2$ -receptor occupancy, and safety profile from previous trials (see [Section 4.3.1](#)). In Trial CVL-865-HV-001, the exposure-response relationship was demonstrated for PSL-IV total score in which darigabat doses, 7.5 mg BID and 25 mg BID, were tested based on the receptor occupancy. A similar exposure-response was observed for SPV, which is a putative marker for desired  $\alpha 2/3$  GABAA receptor engagement ([Nickolls et al, 2018](#)). That is, as darigabat plasma concentrations increased, the change from Baseline in SPV decreased. Therefore, the 25 mg BID dose will be used to test the therapeutic potential of darigabat as treatment of panic disorder.

The primary endpoint in this trial is the proportion of participants who are free of panic attacks during the last 2 weeks of the Maintenance Treatment Period. It has been demonstrated that a higher proportion of patients treated with currently approved therapies were free of panic attacks than those treated with placebo at the end of treatment period ([Paroxetine Prescribing Information](#); [Fluoxetine Prescribing Information](#); [Venlafaxine Prescribing Information](#); [Clonazepam Prescribing Information](#); [Alprazolam Prescribing Information](#)). A key secondary endpoint, the PDSS ([Shear et al, 1997](#)), is a 7-item, clinician administered measure of panic disorder severity that covers multiple dimensions of the disorder and has become a widely used standard measure.

The safety assessments are considered standard for evaluation of neurological compounds. The C-SSRS is commonly used for stringent monitoring of the risk of suicidality in clinical trials ([Posner et al, 2011](#)). The PWC is an instrument used to assess BZD-like withdrawal and will be used to monitor for withdrawal symptoms for up to 7 days after the last dose of IMP during the Follow-up Period ([Rickels et al, 2008](#)).

### 4.3. Justification for Dose

#### 4.3.1. Dosing Rationale

Single doses of darigabat up to 100 mg have been safe and well tolerated and associated with mild AEs. No clinically significant findings in ECGs, laboratory results, vital signs, and physical examinations have been observed at doses up to 100 mg. Multiple doses of darigabat up to 42.5 mg BID (2 weeks at target dose) have also been found to be safe and well tolerated in healthy adult participants. At the 25 mg BID dosing level, the common AEs (>25%) reported higher than placebo have been bradyphrenia, dizziness, somnolence, disturbance in attention, fatigue, headache, and constipation. Most AEs were mild. Dose titration may mitigate the occurrence of central nervous system AEs.

The results from Trial CVL-865-HV-001 demonstrated an exposure-response for PSL-IV total score. As darigabat plasma exposure increased, the placebo-corrected change in PSL-IV total score decreased, reflecting the anxiolytic effect of darigabat. This response appeared to plateau at higher concentrations suggesting higher doses may not provide additional benefit considering the exposure in this trial was estimated to achieve  $\alpha 2$  and whole brain receptor occupancy of approximately 74% and 85%, respectively, in the 25 mg BID group. A similar exposure response was observed for SPV, which is a putative marker for desired  $\alpha 2/3$  GABAA receptor engagement ([Nickolls et al, 2018](#)). That is, as darigabat plasma concentrations increased, the change from Baseline in SPV decreased.

Based on the safety, tolerability, PK/PD profile, and anxiolytic results from completed Phase 1 and 2 trials, the dose that will be used in this trial is a maintenance dose of 25 mg BID after an initial approximately 2-week titration period to target dose (see [Table 3](#)).

